## 1.0 Objectives/Specific Aims

**Objective:** To evaluate the impact of increased frequency and intensity of Physical Therapy (PT) services on patient outcomes in the acute stroke population

### Aims & Hypotheses:

**Aim 1:** To determine the impact of increased frequency and intensity of PT services compared to the usual care PT on discharge disposition of patients post-stroke.

**Hypothesis 1:** We hypothesize that patients receiving an increased frequency of PT services will have higher rate of discharging to home/acute rehabilitation center than to a subacute rehabilitation/skilled nursing facility compared to patients in the usual care PT group.

**Aim 2:** To determine the impact of increased frequency and intensity of PT services, as opposed to usual care, on functional mobility.

**Hypothesis 2:** We hypothesize that patients in the treatment physical therapy group will demonstrate higher degree of improvement on the Activity Measure for Post Acute Care (AMPAC) and Postural Assessment Stroke Scale (PASS) from admission to time of discharge from the hospital and at 90-day follow up. We also expect lower overall Modified Rankin Scale (mRS) scores for the increased frequency PT group compared the usual care PT group at three months post stroke.

**Aim 3:** To ensure that high frequency dosage is safe and feasible to implement the proposed PT regimen in the acute inpatient setting.

**Hypothesis 3:** We hypothesize that there will be fewer adverse events experienced by patients in the increased frequency compared to the usual care group.

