##### **Inclusion Criteria:**

Acute stroke

NIH Stroke Scale score of 2-18 with motor involvement

Age </=80yo

Medical stability for increased therapy services, determined by Stroke Service NP

Ability to give informed consent

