## **8.0 Recruitment methods:**

Potential subjects will be identified via chart review on admissions to the stroke service and appropriateness of enrollment will be decided by PI based on discussion with the patient's clinical care team. Consent will be obtained by PT on initial evaluation. The PI/study team will already be part of these patients' clinical care and the PT or nurse practitioner obtaining consent will be an approved member of the study team on the eIRB application.

This study will also recruit from the Registry for Stroke Recovery (RESTORE-Pro#00037803, IRB approved 9/6/14) which is a research tool sponsored by the National Institutes of Health (NIH) Center of Biomedical Research Excellence (COBRE) in Stroke Recovery with subjects consented for future contact to support stroke recovery research conducted at MUSC. RESTORE staff will query the registry for potential subjects and provide the Principal Investigator (PI) with the contact information of subjects who meet their criteria. The PI or research staff will contact subjects to further screen for potential enrollment.

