## **10.0 Study Design:**

This study will be designed as a randomized control trial with a 1:1 randomization. This study will utilize a permuted block design to randomly allocate a participant to a treatment group, while maintaining a balance across treatment groups. All patients will be identified and consented within 24 hours of admission.

The treatment group will receive increased frequency of PT services within the first 3-5 days of admission, followed by daily PT services for the duration of their inpatient stay. As part of the increased intensity of the treatment provided- this group will receive error augmentation training where the treating therapist will induce errors throughout mobility to challenge the patients rather than facilitating error-free movement. The deficits identified on evaluation will be targeted and emphasized throughout all therapy sessions. For patients with hemiparesis, the hemiparetic limb will be resisted during mobility. For patients with balance impairments- balance will be challenged by narrowing the base of support and resisting midline positioning

toward the side of the balance impairment. The treatment as usual group will receive standard care of PT services 3-5 times per week during their hospitalization which focuses on performing bed mobility, transfers and ambulation vs wheelchair mobility as able. Safety will be ensured throughout therapy sessions. Fall risk will be avoided with the use of a gait belt and non-skid socks and cerebral perfusion concerns will be mitigated by checking a resting blood pressure prior to upright mobility. The Postural Assessment Stroke Scale will be obtained as part of the initial PT clinical evaluation, on day three of hospital admission and at 90 day follow up. Follow up will be conducted (at 90 days +/- 15 days) via neurology clinic- either in person, through virtual clinic or, patient will be contacted via password protected Zoom. NIHSS and MRS scores will also be obtained from patient's chart on admission and at 90 day follow up. All of this data will be collected prospectively for both groups for this research study.

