Precaution will be taken to lessen the probability of risks; despite increased frequency of treatments, duration of upright will still be approached cautiously within the first 24 hours s/p stroke for cerebral perfusion. ALL stroke patients will be returned to supine within 24 hours post stroke and maintain head of bed <30 degrees except for medication, meals, and therapy. Therapy will be stopped if patient deemed medically unstable for increased frequency of treatments by the Stroke NP, Attendings, Fellow, or PI; this decision will be documented via "bed rest" orders in the patient's electronic medical chart, so that the study team is aware to avoid progressive frequent upright mobilization.

**Data collection:** Patient data will be collected from their medical record. Data collected from EPIC/patient's MUSC EMR will be coded in the research database. Data collected include:

- 1) Demographics: sex, age, race
- 2) Stroke risk factors: history of HTN, HLD, A-fib, or DM
- 3) Stroke specifics: type of stroke (hemorrhagic vs ischemic), location of stroke, stroke severity (measured by NIHSS & MRS), time of symptoms to presentation, intervention (tPA or thrombectomy) and complications
- 3) Physical Performance and Functional Measures: Postural assessment stroke scale scores on evaluation, day three and 90 day follow up. Discharge disposition recommended vs ultimate discharge disposition, hospital length of stay.

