For the primary outcome, PASS, to test the null hypothesis of no difference between the group versus a MCID of 2.7, at 5% significance level, using a repeated measure designs at 4 time points and an autoregressive correlation of .6, and a standard deviation of 720 with more than 80% power. Although there is power to detect a moderately small difference (2.7 as mentioned), the purpose here is also to estimate the difference between the two randomized groups. Based on the past literature, in similar populations the standard deviation of PASS measurements is at the most 7.20 Using this, with a sample of 75 patients in each group, with 95% confidence at the end of the study we can estimate this difference within a margin of error of 2.3.

We are planning to conduct the analysis using intention to treat paradigm. In a preliminary analysis we will compute all summary statistics. Initial plots, such as spaghetti plots, will be used to guide our analyses. A general linear mixed model approach will be used to analyze all the outcomes. This model will account for the correlations between time points using either a compound symmetric or spatial structure for the covariance matrix. Post-hoc analyses using Tukey type adjustments will be performed to obtain least squares estimates of the differences between the two randomized groups. Although the study is powered based on only the primary outcome (PASS), we will apply multiple comparisons adjustments for the rest of the outcomes, using Bonferroni corrections. We will test for the assumptions using diagnostic procedures and take appropriate actions if needed. Also, we will define an outcome to be 'favorable' or 'unfavorable' based on a threshold and apply generalized linear mixed models with logistic link and repeat the analyses. We will attempt to minimize drop- outs but in case of missing data, we will assume Missing at Random or Missing Completely at Random. If necessary we will perform multiple imputations. For all analyses, we will use SAS, (MIXED, GLIMMIX, MI and MIANALYZE).

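### Pre-stroke residence and pre-stroke disability are neither restricted nor recorded, so the Aim 1 disposition outcome cannot separate return to a prior facility from new institutionalisation

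*Combined protocol and SAP*

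**What the plan says.** - **Outcomes.** Section 1.0, Hypothesis 1, expects the treatment group to have a "higher rate of discharging to home/acute rehabilitation center than to a subacute rehabilitation/skilled nursing facility". Hypothesis 2 expects "lower overall Modified Rankin Scale (mRS) scores for the increased frequency PT group" at three months and names no cut-off.
- **Eligibility.** Section 5.0 has five inclusion items: acute stroke, "NIH Stroke Scale score of 2-18 with motor involvement", age up to 80, medical stability and "Ability to give informed consent". Its six exclusions concern acute instability or bed rest, pregnancy, custody, current COVID-19, inpatient dialysis and external carotid stenting. None refers to residence or function before the stroke.
- **Data collected.** The list in Section 10.0 has three demographic items (sex, age, race), four vascular risk factors, stroke details, PASS, recommended and actual disposition, and length of stay. It includes mRS under "stroke severity (measured by NIHSS & MRS". On timing, the same section says "NIHSS and MRS scores will also be obtained from patient's chart on admission and at 90 day follow up".
- **Allocation and analysis.** Section 10.0 specifies 1:1 permuted blocks and names no stratification factor. The analysis text in Section 11.0 names no baseline covariate. It also plans to "define an outcome to be 'favorable' or 'unfavorable' based on a threshold", without naming the outcome or the threshold.
- **Recruitment.** Section 8.0 adds a second source: "This study will also recruit from the Registry for Stroke Recovery".

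**The concern.** Discharge disposition means different things depending on where the patient came from. Someone who lived in a skilled nursing facility, has a mild stroke, recovers and returns there has gone back to their starting point. Someone who lived at home and is sent to the same facility has lost independence. Hypothesis 1 puts both on the unfavourable side, and nothing in the planned dataset would separate them.

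The mRS raises a related issue. A patient already dependent before the stroke has fewer grades to gain by 90 days. The admission mRS does not clearly supply the missing baseline, because the plan presents it as a measure of how severe the stroke is.

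At stake are the interpretability of the first aim's outcome, some dilution of the disposition contrast, and precision that a baseline covariate would have recovered.

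**Working it through.** **1. The plan's own figures.** Section 11.0 states precision and power for PASS only. With 75 per group, the 95% margin is 1.96 x SD x sqrt(2/75). This gives 2.24 for SD 7 (2.26 with the t quantile) and 2.30 for SD 7.20, in line with the stated 2.3. For the mean of four measurements with autoregressive correlation 0.6, the variance factor is [4 + 2(3 x 0.6 + 2 x 0.36 + 0.216)]/16 = 0.592. Power for a difference of 2.7 is then 86.6% (SD 7) or 84.7% (SD 7.20), consistent with the stated figure above 80%. None of these inputs involves pre-stroke residence or disability. The plan states no rate, power or precision for disposition or mRS, so everything below rests on assumed values.

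**2. Dilution of Aim 1.** Let f be the share of facility residents, assumed to have essentially no chance of the favourable outcome in either arm. A true 15-point difference among the others (assumed) is observed as 15 x (1 - f):

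| f (assumed) | Observed difference, points |
|---|---|
| 5% | 14.3 |
| 10% | 13.5 |
| 15% | 12.8 |

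**3. Precision, at f = 10% and 75% success among the others (both assumed).**
- Overall success rate: 0.90 x 0.75 = 0.675.
- Unadjusted 95% margin: 1.96 x sqrt(2 x 0.675 x 0.325/75) = 15.0 points.
- Margin after removing between-subgroup variation: 1.96 x sqrt(2 x 0.90 x 0.75 x 0.25/75) = 13.1 points.
- Margin in home-dwelling patients only, on average 0.90 x 75 = 67.5 per arm: 1.96 x sqrt(2 x 0.75 x 0.25/67.5) = 14.6 points.

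Ratio of expected difference to margin:
- unadjusted: 13.5/15.0 = 0.90
- adjusted: 13.5/13.1 = 1.03
- home-dwelling only: 15/14.6 = 1.03

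Under these assumptions, adjusting and restricting recover about the same amount.

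**4. Power of an unadjusted comparison.** Assume 65% versus 85% success among the others, a 20-point difference, two-sided 5%, 75 per arm, and multiply both rates by (1 - f). Power = Phi{[d - 1.96 sqrt(2 p(1 - p)/75)] / sqrt([p1(1 - p1) + p2(1 - p2)]/75)}, where d = p2 - p1 and p is the mean of the two rates.

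| f (assumed) | Rates | Power | n per arm for 80% |
|---|---|---|---|
| 0 | 65.0% v 85.0% | 81% | 73 |
| 5% | 61.7% v 80.7% | 73% | 88 |
| 10% | 58.5% v 76.5% | 66% | 106 |
| 15% | 55.2% v 72.2% | 58% | 125 |

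With base rates of 60/80 or 70/90 instead, power at f = 10% is 63% or 69%, against 77% or 87% at f = 0.

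**5. mRS.** No arithmetic applies. Hypothesis 2 compares overall scores, so a previously dependent patient still contributes, over a shorter range. A hard ceiling would arise only if the undefined threshold in Section 11.0 were applied to mRS.

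**The case against.** The case against giving this much weight is substantial, and several stronger readings that a reader might infer do not survive it.

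- **That these patients cannot succeed.** Not supported. Discharge to acute rehabilitation counts as favourable and is not closed to a facility resident, and a dependent patient who lived at home can return home. On mRS there is no defined success to be denied: a patient at grade 4 beforehand can still end at 4 rather than 5. The share f above therefore applies to facility residents only, and giving them zero chance is a worst case.
- **That chance imbalance passes almost one for one into the result, on top of ordinary error.** Not supported. At f = 10%, the 95% range for imbalance in the subgroup's share is 1.96 x sqrt(2 x 0.10 x 0.90/75) = 9.6 points. At 75% success among the others it moves the disposition difference by 0.75 x 9.6 = 7.2 points, and that is already inside the 15.0-point margin. The recoverable part is about 2 points. With randomisation there is no systematic bias.
- **That registry recruitment enriches for such patients.** Speculative. The documents give no recurrent-stroke share, and a registry member newly admitted with a stroke would also be found by the chart review of admissions in Section 8.0.
- **That the information is lost for good.** Too strong. Study data come from the medical record and a linking file is kept, so later abstraction is possible for whatever the chart holds. It would not be a prespecified, pre-allocation variable.
- **That facility residents should be excluded.** This has a cost: it would also remove them from the primary PASS analysis, where they can respond.

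The age limit, NIHSS range and consent requirement probably keep the share low. It is also fair that the plan never says explicitly how a return to a prior facility is coded; scoring it as unfavourable is the literal reading of Hypothesis 1.

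What stands is the gap itself: no criterion, no field and no covariate.

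**Conclusion.** The point holds as a low-cost improvement. The plan neither restricts nor records pre-stroke residence or disability, and the admission mRS is not a stated substitute. As planned, the disposition outcome mixes return to baseline with new institutionalisation.

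The size depends on an unknown share. At an assumed 5-15% facility residents with little chance of the favourable outcome, a 15-point difference shrinks to about 14.3-12.8 points. At 10%, the 95% margin is about 15.0 points unadjusted against 13.1 adjusted. These figures also rest on the assumed 15-point effect and 75% success rate. If the share is near zero, the statistical loss is negligible and only the ambiguity of the outcome remains.

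The effect is confined to Aim 1 and mRS. It does not bias the randomised comparison or alter the PASS sample size.

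**What to change.** 1. **Section 10.0, data collection:** add pre-stroke residence and pre-stroke mRS, taken from the chart or the patient and recorded before allocation. State that the admission mRS is a separate, post-stroke value.
2. **Section 5.0:** leave eligibility unchanged, so that these patients stay in the primary PASS analysis.
3. **Section 11.0, disposition:** adjust the Aim 1 analysis for pre-stroke residence, or add a prespecified Aim 1 analysis in patients living at home before the stroke. State how a return to a prior facility is classified. If almost no facility resident has the favourable outcome, the residence term in a logistic model may not be estimable; a risk difference stratified by residence avoids this.
4. **Section 11.0, mRS:** use pre-stroke mRS as a covariate for 90-day mRS.

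The cost is two extra chart fields, a few sentences in the analysis text, and slightly fewer patients in the restricted Aim 1 analysis if that option is chosen.

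### The 90-day mRS difference should not be tested with a variance pooled with admission: under the planned covariance structures, the level of that test depends on a variance ratio the documents do not give

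*Combined protocol and SAP*

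**What the plan says.** Section 1.0 (Aims & Hypotheses), Hypothesis 2, sets an expectation for the mRS at a single time, three months after stroke: "We also expect lower overall Modified Rankin Scale (mRS) scores for the increased frequency PT group compared the usual care PT group".

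Section 10.0 (Study Design) gives the mRS two measurement times: "NIHSS and MRS scores will also be obtained from patient's chart on admission and at 90 day follow up".

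The statistical text, under Section 11.0 (Data Management), makes no separate provision for the mRS: "A general linear mixed model approach will be used to analyze all the outcomes". Correlation between time points is to be modelled "using either a compound symmetric or spatial structure for the covariance matrix". Post-hoc work is meant "to obtain least squares estimates of the differences between the two randomized groups", without saying at which visit, or whether as a level, a change or an average. For outcomes other than PASS, "we will apply multiple comparisons adjustments for the rest of the outcomes, using Bonferroni corrections"; their number is not given.

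The same text adds a favorable/unfavorable logistic mixed model with no threshold stated, exploratory plots, and a general undertaking to check assumptions and respond. It names no unstructured, heterogeneous-variance or ordinal model. It does not say whether admission mRS is a response or a covariate.

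**The concern.** With only two visits, the choice between the permitted structures makes no difference: in standard form each has one variance and one correlation. The model therefore estimates a single variance from admission and 90-day scores together and applies it to the 90-day group difference.

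The two spreads need not be alike. Section 5.0 restricts entry to NIHSS 2-18 with motor involvement, which may compress the admission mRS, while 90-day scores may spread over the scale. If so, the standard error and confidence interval for the three-month difference are too narrow, and a false claim of lower disability is more likely than the stated level allows. Bonferroni would then be applied to a p-value that is already too small.

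**Working it through.** **Plan's own figures.** There is none for the mRS. For PASS, with SD 7 and 75 per arm, the 95% margin is 1.96 × 7 × √(2/75) = 2.24 (2.26 with a t quantile; 2.30 with SD 7.2), against the stated 2.3. The sample size is therefore read correctly.

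**Is baseline a response row?** The PASS power statement counts four time points. Section 4.0 lists PASS at evaluation, day three, discharge and 90 days. Four is reached only by counting the evaluation, so baseline is a response in that model. The analysis text names no covariate. Carried over to the mRS, admission becomes a response, although the plan does not say so outright.

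**Inputs.** n = 75 per arm, 1:1; two mRS visits; 5% level (stated for PASS: "to test the null hypothesis of no difference between the group versus a MCID of 2.7, at 5% significance level"), taken as two-sided because sidedness is not given. Let v0 and v1 be the admission and 90-day variances, c their covariance, and q = SD at admission / SD at 90 days. q is an assumption.

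**Derivation, complete data.** Under a two-visit common-variance model, the sum and the difference of a patient's two scores are uncorrelated. Their variances are estimated by v0 + v1 + 2c and v0 + v1 − 2c. The common variance is a quarter of their total: (2v0 + 2v1)/4 = (v0 + v1)/2.

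- *90-day difference:* the model uses (v0 + v1)/2 where v1 is correct. Model SE / true SE = √((1 + q²)/2).
- *Change from admission:* the model variance is v0 + v1 − 2c, which is correct, so its level holds.
- *Average over both visits:* the model variance is (v0 + v1 + 2c)/4, also correct. But therapy cannot alter the admission score, so this contrast halves any 90-day effect.

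True size of the 90-day test = 2 × [1 − Φ(z × √((1 + q²)/2))], where z is the two-sided critical value.

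Example, q = 0.5: √(1.25/2) = 0.791; 1.96 × 0.791 = 1.55; size = 12.1%.

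| q | Nominal 5% | Nominal 0.83% (Bonferroni, 6 outcomes assumed) |
|---|---|---|
| 0.5 | 12.1% | 3.7% |
| 0.6 | 10.6% | 3.0% |
| 0.7 | 9.1% | 2.3% |
| 0.8 | 7.6% | 1.7% |
| 0.85 | 6.9% | 1.4% |
| 1.0 | 5.0% | 0.83% |
| 1.25 | 2.7% | 0.28% |
| 1.5 | 1.3% | 0.08% |

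For q from 0.85 to 0.5, the SE is 0.93 to 0.79 of its proper value. The relative inflation is 6.9/5 = 1.4 to 12.1/5 = 2.4 times at 5%, and 1.4/0.83 = 1.7 to 3.7/0.83 = 4.5 times at the corrected level. Constraining the arms to a common admission mean gives the same sizes.

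**Simulation.** Correlated 0-6 scores, 75 per arm, no effect, assumed latent correlation 0.5, 20,000 trials per setting, nominal 5%:

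| SD admission / SD 90 days | Common-variance 90-day test |
|---|---|
| 0.90 / 1.76 | 11.6% |
| 1.17 / 1.76 | 9.5% |
| 1.45 / 1.76 | 7.3% |
| 1.45 / 1.48 | 5.0% |
| 1.92 / 1.48 | 2.4% |

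Across all simulated settings, a t-test of the 90-day mRS alone ran at 4.7-5.2%, a Wilcoxon test of the 90-day mRS alone at 4.7-5.2%, and the change contrast at 4.8-5.2%. A fitted proportional-odds Wald test ran at 5.1% (1,500 trials).

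**The case against.** **Admission mRS may be a covariate.** The data-collection list in Section 10.0 places the mRS with stroke severity, not with the functional measures. As a covariate it leaves one post-baseline score and nothing to pool. This stands as a possible reading, but the four-visit PASS model points the other way and the text does not settle it.

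**The contrast is not named.** This also stands. A change contrast would hold its level. Hypothesis 2, however, words the mRS expectation as a three-month level.

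**The direction is assumed.** Patients with NIHSS as low as 2 are eligible, so admission mRS need not be tightly bunched. The simulations run from 2.4% to 11.6%. A reader might infer that the planned test does run at 7-12%; the documents give no mRS distribution and do not support that.

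**An ordinal scale needs an ordinal model.** A reader might take the ordinal scale to be the cause. It is not, because a plain t-test at 90 days also holds 5%. Nor does power make the case: with an assumed common odds ratio of 2 and 75 per arm, simulated power was 62-66% for the t-test and 65-67% for Wilcoxon.

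**Safeguards exist.** Plots and diagnostics could reveal unequal spreads, but no fallback is named, so any repair would be chosen after seeing the data. The logistic analysis has no threshold and does not correct the linear test. Bonferroni lowers the absolute rate: with six outcomes assumed, it stays below 5% over the range shown. The test still exceeds its own share whenever q is below 1.

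**Conclusion.** The point holds conditionally. It needs three things: admission mRS as a response (implied, not stated), the 90-day difference as the tested contrast (matching Hypothesis 2, not named in Section 11.0), and unequal visit variances (unknown). Given these, a nominal 5% test runs at about 7-12% for an admission SD of about 0.85 down to 0.5 of the 90-day SD. It is exact at equal SDs and conservative when the admission SD is the larger.

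The documents do not support reading this as a demonstrated false-positive rate above 5% for the mRS, which is a non-primary outcome under Bonferroni. They do show a plan that lets the level of a hypothesised test depend on an unneeded equal-variance assumption. This is a cheap improvement, not a flaw that undermines the trial.

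**What to change.** In the statistical text of Section 11.0, take the mRS out of the general repeated-measures model and do one of the following:

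1. Test the 90-day mRS alone, with admission mRS or NIHSS as covariate. Nothing is then pooled across visits. A cumulative-logit model in GLIMMIX, already named in the plan, suits this analysis because the mRS is ordinal.
2. If both visits stay as responses, use an unstructured or heterogeneous-variance covariance and name the 90-day group difference as the contrast that tests Hypothesis 2.

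The cost is a few lines of wording, with no new data or software. The cumulative-logit form has a small downside: it reports a common odds ratio, not a mean difference, and proportional odds must be checked.
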